8.1.2 Prior and Concomitant Medications

Any treatments/medications taken for HD during the time between the end of the Phase 1b/2a study and the patient signing the ICF for the OLE study will be recorded in the patient's eCRF.

All concomitant medications used from the time the patient signs the OLE ICF to the end of the patient's participation in the OLE study will be recorded in the patient's eCRF.

The minimum requirement is that the drug name, dose, indication, and the dates of administration are recorded. This will include all prescription drugs, herbal products, vitamins, minerals, and over-the-counter medications. Any changes in concomitant medications will also be recorded in the patient's eCRF.

Any concomitant medication deemed necessary for the welfare of the patient during the study may be given at the discretion of the Investigator. However, it is the responsibility of the Investigator to ensure that details regarding such medication are recorded in full in the eCRF.

8.1.2.1 Restricted Concomitant Medications

Use of all antiplatelet (e.g., aspirin, prasugrel, etc.) or anticoagulant (e.g., heparin, warfarin, etc.) therapy is restricted throughout the study. Patients who take antiplatelet therapy will need to complete a 7-day washout period before undergoing intrathecal administration of the study drug. Patients who receive most anticoagulant therapies will need to complete a 1-day washout period before undergoing intrathecal administration of the study drug. However, because of the longer plasma half-life, patients taking warfarin will need to complete a 5-day washout period before undergoing intrathecal administration of the study drug.

8.1.3 Physical Examination

A physical examination will be performed at the time points noted in the Schedule of Assessments ([Section 4.2](#)).

Immediately postdose (through 4 hours postdose), a targeted physical exam to assess potential motor effects will be performed. This exam will include a neurologic examination with special attention to the motor system, and upper and lower extremity measures of strength, tone, reflexes, and ambulation.

At all other time points, the physical exam must include (at a minimum) head, eyes, ears, nose, throat, respiratory, cardiovascular, gastrointestinal, musculoskeletal, psychiatric, and neurologic systems. Other systems should be evaluated as appropriate.

Physical findings will be recorded in the eCRF and source documents.

8.1.4 Vital Signs

Blood pressure (systolic and diastolic), temperature, and pulse will be measured by medically qualified personnel at the time points described in the Schedule of Assessments (Section 4.2) and recorded in the eCRF and source documents. Vital signs measurements will be taken as per standard site practice, after the patient has been resting quietly (either lying flat or sitting, whichever is most appropriate for the condition of the patient) for a period of at least 3 minutes. As feasible, the same position (either sitting or lying) should be used for all subsequent vital signs measurements during the study for an individual patient. If the initial reading is high, the measurements will be repeated twice and the average of the 3 readings will be used.

8.1.5 Height and Weight

The patient's height and weight will be measured at the time points described in the Schedule of Assessments (Section 4.2) and recorded in the eCRF and source documents.

8.1.6 12-Lead ECG

Computerized, good quality, 12-lead ECGs will be recorded in triplicate at the time points described in the Schedule of Assessments (Section 4.2). Recordings will be obtained in the supine position after the patient has rested comfortably for ≥ 5 minutes.

The ECG tracing will be submitted and read by a centralized reviewer (details will be provided in the ERT[®] Study Manual). The following should be recorded on the trace and eCRF: whether the ECG is normal or abnormal and, if deemed abnormal, whether the abnormality is clinically significant or not clinically significant, with the abnormality noted.

8.1.7 Clinical Laboratory Evaluations

Clinical laboratory safety testing will be collected at the time points described in the Schedule of Assessments (Section 4.2) and recorded in the eCRF and source documents. A blood sample will be tested locally up to 1 week prior to the lumbar puncture to determine platelet count and prothrombin time, and thereby confirm that it is safe to proceed with the lumbar puncture. Other safety laboratory samples will be analyzed at a central laboratory. Local testing on these samples may be conducted as clinically indicated.

The parameters to be assessed are presented in Table 3.

Table 3 Clinical Laboratory Parameters

Hematology	Coagulation	Clinical chemistry	Urine dipstick
Complete blood count, including: 
 • White blood cell count (with differential) • Red blood cell count • Hemoglobin • Hematocrit • Platelet count • Reticulocyte count • Mean corpuscular volume • Mean corpuscular hemoglobin • Mean corpuscular hemoglobin concentration Measures of Inflammation, including: 
 • High Sensitivity C-reactive protein • Complement 	Activated partial thromboplastin time Prothrombin time Fibrinogen	Sodium Potassium Chloride Bicarbonate Blood urea nitrogen Creatinine Creatine phosphokinase Alanine aminotransferase Aspartate aminotransferase Alkaline phosphatase Bilirubin	Urinalysis

8.1.8 Cerebrospinal Fluid Safety Lab

A CSF safety laboratory sample obtained at the times noted on the Schedule of Assessments (Section 4.2) will be evaluated at a local lab. The following parameters will be assessed: total protein, glucose, and cell counts (white blood cell counts with differential).

8.1.9 Suicidality Assessment (Columbia-Suicide Severity Rating Scale)

The C-SSRS is a measure of suicidal ideations and suicidal behaviors²⁰. The C-SSRS is provided in Appendix 1. The ‘since last visit’ form, will be performed at all time points noted in the Schedule of Assessments (Section 4.2). A trained rater will complete this scale. The findings should be confirmed by the clinical opinion of the Investigator.

The Investigator should be notified if a patient responds “yes” to any of the questions. The Investigator will provide care according to local standards, which may include referral to specialists, medical treatment, or hospitalization as necessary.

8.1.10 Pregnancy Testing

For female patients of childbearing potential, a negative serum pregnancy test must be documented at the Screening Visit and a negative urine pregnancy test must be documented at the times noted on the Schedule of Assessments (Section 4.2). The serum pregnancy test will be determined by a central lab; urine pregnancy tests will be performed locally.

8.1.11 Drug Screening

A urine drug screen for opioids, cocaine, amphetamines, methadone, barbiturates, methamphetamine, and phencyclidine will be performed at the times noted on the Schedule of Assessments (Section 4.2). Drug screen tests will be evaluated by a central laboratory.

8.2 Pharmacokinetic Assessments

Samples for analysis of PK of WVE-120101 and WVE-120101-related metabolite excretions in plasma and urine and concentrations of WVE-120101 in CSF will be collected at the time points specified on the Schedule of Assessments (Section 4.2). The date and time of the sample collection will be recorded.

Patients who are entering the study may be requested to consent to two additional lumbar punctures (LP) to provide CSF samples at two weeks after the first dose, and two weeks after the sixth dose to allow for more robust PK/PD modeling (see Table 1 for more details). These additional CSF samples will be optional, and consent will be collected as a stand-alone question in the Informed Consent Form. If a patient has already passed the first dose, but not the sixth, and is willing to undergo the additional LP, then CSF will be collected 2 weeks after the sixth dose.

In addition to the above two CSF samples, patients at certain participating sites will undergo additional intensive PK blood and urine sampling as noted in Table 2. This sampling will include additional time points for plasma and a 24-hour urine collection.

Samples will be analyzed by a central laboratory to determine concentrations of WVE-120101 using a validated method.

8.3 Pharmacodynamic Assessments

A CSF sample will be collected at the time points noted in the Schedule of Assessments (Section 4.2) to determine the change from baseline in concentration of mHTT protein. In addition, NFL and other exploratory biomarkers in CSF, plasma, and serum may be assessed.

The study may utilize the method described in Wild et al.²¹ or an alternative method to determine levels of mHTT protein.

8.4 Immunogenicity Assessments

Serum samples will be collected at the times noted on the Schedule of Assessments (Section 4.2) and analyzed at a central laboratory for measurement of anti-drug antibodies to WVE-120101.

8.5 Magnetic Resonance Imaging

A 3 Tesla (3T) MRI of the whole brain (without contrast) will be performed at the time points noted on the Schedule of Assessments (Section 4.2). Sedation is permitted during the MRI. All other eligibility should be confirmed prior to the MRI scheduled at the Screening visit.

The MRI will be assessed for safety purposes, in addition to exploratory structural assessments. Exploratory assessments will include, but are not limited to, volumetric assessments. Changes in MRI of the brain will be characterized in patients receiving WVE-120101.

The MRI will be performed by an appropriately trained individual. Detailed instructions on how the MRI will be performed and transferred to the central reader are provided in the Imaging Manual. The scans will be evaluated by a central reader.

8.6 Assessment of Clinical Effects

8.6.1 Unified Huntington's Disease Rating Scale

The Unified Huntington's Disease Rating Scale (UHDRS) is a research tool developed by the Huntington Study Group to provide a uniform assessment of the clinical features and course of HD²². The scale consists of 6 subtests, including motor assessment, cognitive assessment, behavioral assessment, an independence scale, functional assessment, and TFC, and is provided in [Appendix 2](#). In addition, analyses will be performed using the composite UHDRS (cUHDRS), which is based on 4 of the UHDRS components, namely the TFC, Symbol Digit Modalities Test (SDMT), Stroop Interference test, and the total motor impairment score²³. All subtests of the UHDRS should be performed except the behavioral assessment, as the PBA-s ([Section 8.6.2](#)) collects similar behavioral information.

The motor assessment evaluates motor features of HD with standardized ratings of oculomotor function, dysarthria, chorea, dystonia, gait, and postural stability. The total motor impairment score is the sum of all the individual motor ratings, with higher scores indicating more severe motor impairment than lower scores.

The cognitive assessment consists of a lexical verbal fluency test, SDMT, and the Stroop Interference test. The Stroop Test results are reported as the raw number of correct answers given in a 45-second period. Results for the other tests are reported as the raw number of correct responses. Higher scores indicate better cognitive performance.

The independence scale is used to follow disease progression in functional disability. The scale is rated from 100 (no special care needed) to 0 (tube-fed, total bed care).

The functional assessment checklist is a 25-question assessment that screens for capacity to complete the tasks mentioned in the assessment. The questions are asked in the presence of a family or friend to get the clinician's best judgment based on both responses. A response of "yes" is given a score of 1. A higher score indicates better functioning.

The TFC is a brief interview involving the patient and a close family member or friend familiar with the patient's functioning. The measure has 5 items and addresses basic activities of living: occupation, handling finances, domestic responsibilities, activities of daily living (e.g., eating, dressing, bathing), and level of care.

8.6.2 Short Problem Behaviors Assessment

The PBA-s is a shorter version of the Problem Behaviors Assessment for HD (PBA-HD), a semi-structured interview designed to elicit information about behavioral symptoms relevant to HD. The shorter version was developed by the Behavioral Phenotype Working Group of the European Huntington's Disease Network (EHDN)²⁴, and is contained in [Appendix 3](#).

The PBA-s contains 11 items, each measuring a different behavioral problem that is rated for both severity and frequency on a 5-point scale. Severity and frequency ratings are multiplied to provide an overall score for each symptom.

Interviews are conducted with the patient. The final rating is determined by assessing all available information, including the interviewer's own observations of the patient's behavior. A caregiver should not be interviewed as part of the PBA-s for this study.

9 ADVERSE EVENTS

The Investigator is responsible for reporting all AEs that are observed or reported during the study, regardless of their relationship to study treatment or their clinical significance.

Adverse event information will be collected beginning at enrollment (date of signed informed consent) and up to the end of the study. All ongoing AEs at the end of the study will be followed to resolution, or until the Investigator and the Sponsor agree that further follow-up is not required.

An AE is defined as any untoward medical occurrence in a patient enrolled into this study regardless of its causal relationship to study treatment. Patients will be instructed to contact the Investigator at any time after Screening if any symptoms develop.

A TEAE is defined as any event not present before exposure to study treatment or any event already present that worsens in either severity or frequency after exposure to study treatment.

9.1 Eliciting and Documenting Adverse Events

All AEs reported or observed during the study, including AEs resulting from concurrent illnesses, reactions to concurrent medications, or progression of disease states, will be recorded on the AE page in the eCRF and in the site source notes. The eCRFs used to document AEs are designed to help ensure this information is collected in a standard way. Information to be collected includes event term, date and time of onset, date and time of resolution, Investigator-specified assessment of severity and relationship to study treatment, action taken with respect to study treatment, seriousness, any required treatment or evaluations, and outcome. All AEs will be followed to adequate resolution. The sites will be provided with completion guidelines for the eCRF, which will further guide them on how to record the data, including AEs.

Any medical condition that is present at the time the patient is screened but does not worsen should not be reported as an AE. However, if it worsens at any time during the study, it should

be recorded as an AE. This includes any spontaneously reported worsening of depression, i.e., not based on the study rating scales.

In addition to observations of the patient, AEs identified from any study data (e.g., laboratory values, physical examination findings, ECG changes) or identified from review of other documents that are considered clinically significant will be documented on the AE page in the eCRF. Worsening of symptoms that are only detected on clinical effects rating scales will not be reported as AEs.

Adverse events will be assessed at each visit by direct questioning as well as elicited from physical examination by site staff. In addition, all sites in the study must ensure patients have a 24-hour telephone number to contact medical site staff for the duration of the study, in case of emergent AEs or SAEs.

If there is any doubt as to whether a clinical observation is an AE, the event should be reported.

9.2 Definitions of Adverse Event Severity and Relationship to Study Drug

9.2.1 Severity

The severity, or intensity, of an AE refers to the extent to which an AE affects the patient's daily activities. Adverse event severity will be evaluated using the criteria described in [Table 4](#).

Table 4 Definitions of AE Severity

AE Severity	Definition
Mild	Mild; asymptomatic or mild symptoms; clinical or diagnostic observations only; intervention not indicated.
Moderate	Moderate; minimal, local or noninvasive intervention indicated.
Severe	Severe or medically significant but not immediately life-threatening; hospitalization or prolongation of hospitalization indicated; disabling; limiting self-care.

Abbreviations: AE = adverse event.

Changes in the severity of an AE should be documented in the eCRF to allow an assessment to be performed of the duration of the event at each level of severity.

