3 STUDY OBJECTIVES

Primary Objective:

The primary objective of this study is to evaluate the safety and tolerability of long-term exposure to WVE-120101 in patients with early manifest HD.

Secondary Objectives:

The secondary objectives of this study are to evaluate the clinical and pharmacodynamic effects of WVE-120101 in patients with early manifest HD.

Exploratory Objectives:

The exploratory objectives are:

- To evaluate the PK of WVE 120101 in plasma
 - To evaluate WVE-120101 related excretion in urine
 - To evaluate the exposure of WVE-120101 in CSF
-

- To evaluate the effect of WVE-120101 on exploratory biomarkers

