4.3 Study Endpoints

Safety Endpoints:

The number of patients with AEs, severity of AEs, number of patients with SAEs, clinically significant changes in laboratory values, and the number of patients who withdraw due to AEs.

Clinical Effects Endpoint(s):

- Change from baseline in the Total Functional Capacity (TFC), administered as part of the Unified Huntington's Disease Rating Scale (UHDRS)
- Change from baseline in the motor, cognitive, independence, and functional assessments administered as part of the UHDRS
- Change from baseline in the composite UHDRS (cUHDRS)
- Change from baseline in the Short Problem Behaviors Assessment (PBA-s)

Pharmacodynamic Endpoints:

- Change from baseline in the concentration of mHTT protein in CSF
- Changes from baseline MRI of the brain
- Change from baseline in exploratory biomarkers, including but not limited to neurofilament light (NFL)

PK Endpoints:

- PK parameters of WVE-120101 in plasma
- WVE-120101 and WVE-120101-related metabolite excretions in urine
- Concentration of WVE-120101 in CSF

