9.3 Serious Adverse Events

9.3.1 Serious Adverse Event Criteria

An SAE is defined as any event that results in death, is immediately life threatening, requires inpatient hospitalization or prolongation of existing hospitalization, results in persistent or significant disability/incapacity, or is a congenital anomaly/birth defect not present at Prescreening. Important medical events that may not result in death, be life threatening, or require hospitalization may be considered SAEs when, based upon appropriate medical judgment, they may jeopardize the patient or may require medical or surgical intervention to prevent one of the outcomes listed in this definition. Examples of such medical events include allergic bronchospasm requiring intensive treatment in an emergency room or at home, blood dyscrasias or convulsions that do not result in inpatient hospitalization, or the development of drug dependency or drug abuse. A life-threatening event does not include an AE that, had it occurred in a more severe form, might have caused death.

Serious AEs must be reported ([Section 9.3.4](#)) and will be followed through the follow-up visit. Serious AEs that occur after the final follow-up visit need not be reported unless the Investigator considers them related to study drug.

The Sponsor clinical physician will provide a Sponsor causality statement for all SAEs.

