Adverse event incidence tables will present, by SOC and preferred term, the number and percentage of patients experiencing an AE by severity and by relationship to treatment. In tabulating the severity of adverse events, the highest severity will be assigned to a subject with more than one occurrence of the same adverse event. The highest level of association will be reported in subjects with differing relationships for the same adverse event.

Similar tables will be generated summarizing repeat dosing TEAEs. Listings of all AEs, SAEs, deaths, and AEs leading to study discontinuation will be provided.

Clinical Laboratory Evaluations

Summary statistics of laboratory variables including CSF safety laboratory variables will be calculated for each visit or study assessment by dose group. Laboratory data will also be categorized as low, normal, or high based on the reference ranges of the central laboratory. Frequencies and percentages will be presented by dose group for the shifts in these categories from baseline to post-baseline assessment time points. A listing of clinically significant hematology and chemistry findings will be provided.

Other Safety Evaluations

Summary statistics of vital signs, ECG, and height and weight variables will be calculated for each visit or study assessment by dose group.

Columbia-Suicide Severity Rating Scale

Listings of patients who respond “yes” to item 4 or 5 on the C-SSRS at any point in the study will be provided.

Immunogenicity

Anti-drug antibody assay results to WVE-120101 will be described categorically. Summary statistics for anti-drug antibody titer results will be provided.

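### The AE severity scale in Table 4 has no level for immediately life-threatening or fatal events, so the by-severity tables have no valid grade for them

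*Combined protocol and SAP*

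**What the plan says.** Section 9.2.1 makes Table 4 the instrument for grading: "Adverse event severity will be evaluated using the criteria described in" that table. It has three levels: Mild, Moderate and Severe. The definition of the highest opens with "Severe or medically significant but not immediately life-threatening" and continues with clauses on hospitalization, disability and limited self-care. The abbreviations footnote follows that row directly.

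Section 9.1 lists the data collected for AEs, including the "Investigator-specified assessment of severity and relationship to study treatment". Section 9.3.1 defines an SAE as "any event that results in death, is immediately life threatening, requires inpatient hospitalization", and then gives further criteria.

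Section 3 states the purpose: "The primary objective of this study is to evaluate the safety and tolerability of long-term exposure to WVE-120101" in early manifest HD. Section 4.3 lists the safety endpoints, beginning "The number of patients with AEs, severity of AEs, number of patients with SAEs". Section 10.4.2 plans incidence tables by severity within system organ class and preferred term. Its rule for repeated events is that "the highest severity will be assigned to a subject with more than one occurrence of the same adverse event".

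**The concern.** A severity scale used for tabulation has to be exhaustive: every event must fall in one level. This one stops short at its worst end. The top level carries a clause that shuts out immediately life-threatening events, and no level above it takes them in. That clause makes sense only on a scale with a higher level.

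At stake is the consistency of one safety endpoint. If a life-threatening event occurs, one site may leave the field empty and another may enter Severe despite the definition. The highest-grade rule in Section 10.4.2 would then work on data recorded under two conventions, for the events a reader of the severity tables most wants to see.

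**Working it through.** No arithmetic applies. The documents give no figure on this point to reproduce, so the check compares definitions.

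1. **Are the events in scope?** Yes. Section 9.3.1 names death and immediate threat to life as its first two criteria for seriousness. Section 9.1 collects severity for AEs without exempting serious ones.

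2. **Which level of Table 4 takes them?**

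| Level | Condition in Table 4 (paraphrased) | Immediately life-threatening event | Fatal event |
|---|---|---|---|
| Mild | No or slight symptoms, no intervention needed | Does not fit | Does not fit |
| Moderate | Only limited, noninvasive intervention needed | Does not fit | Does not fit |
| Severe | First clause rules out an immediate threat to life | Expressly excluded | Not named; excluded by implication where the event was an immediate threat to life |
| Higher level | None exists | – | – |

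3. **Can the later clauses of Severe admit them?** The definition goes on to hospitalization, disability and limited self-care, separated by semicolons. If these are alternatives, a life-threatening event that leads to hospitalization could enter that way, although the first clause turns it out. If they qualify the first clause, it cannot enter at all. The text does not say which is meant. A sudden death without hospitalization fits none of them clearly on either reading.

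4. **Does any other section assign a grade?** No. Sections 9.1, 9.3.1, 9.3.4 and 10.4.2 and the synopsis give no severity level for a fatal or life-threatening event.

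5. **Where is the grade used?**
 - In the by-severity TEAE tables of Section 10.4.2, and in the matching tables for repeat-dosing TEAEs.
 - In Section 9.2.1, which asks for changes in severity to be recorded so that time spent at each level can be assessed. An event that passes from Severe to life-threatening has no level to move to.
 - In the TEAE definition of Section 9, which counts worsening in severity of an event already present. Worsening beyond Severe cannot be shown by grade.

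6. **Where are the events captured in other ways?** Section 9.1 collects seriousness and outcome. Section 9.3.4.1 requires an SAE report within 24 hours, with the seriousness criteria. Section 10.4.2 tabulates treatment-emergent SAEs by dose group and lists SAEs and deaths. None of these uses Table 4.

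Steps 2 to 4 show that the scale is not exhaustive. Steps 5 and 6 show that the consequence stays within severity grading and the output built on it.

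**The case against.** The strongest reply is that nothing important is lost. A fatal or life-threatening event is reported promptly as an SAE with its seriousness criterion, counted in the SAE tables and listed, and a death appears in its own listing. The overall incidence tables count the patient whatever the grade. Section 9.2.1 describes severity as the extent to which an event affects daily activities, which points an investigator to the top level. Most life-threatening events would also meet the hospitalization or disability wording. In practice, then, they would probably be entered as Severe. Section 9.1 also promises eCRF completion guidelines, which may settle the matter. A three-level scale is not an error in itself.

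Much of this stands. A reader might infer that the worst events disappear from the safety report or cannot be told apart from other severe events. The seriousness and outcome data and the listings do not support that. A reader might also infer that they will be absent from the severity tables. That is possible but not shown, since entry as Severe is at least as likely.

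The objection does not remove the gap. Seriousness and severity are separate fields, so a correct SAE table does not make the severity table correct. Entering Severe means overriding the first clause of its definition. The completion guidelines are not among the documents and cannot be assumed to override a protocol definition. The fault is not the number of levels, but that the top one excludes what should lie within or above it.

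**Conclusion.** The point holds: Table 4 is wrong as written, because fatal and immediately life-threatening events have no valid severity grade. The defect is confined to the severity endpoint and its tables, and its priority is modest. Those tables are descriptive, and no test, confidence interval or decision rule stated in these documents depends on the grade.

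Two stronger readings should be avoided. The first is that a primary endpoint is compromised. Safety is the primary objective, but Section 4.3 lists severity among several safety endpoints and labels none of them primary. The second is a numerical size. Dividing one event by the planned enrolment, or by the size of a dose group, gives only the weight of one patient. It is neither an error rate nor an expected count. The documents give no rate for such events, and equal dose groups would arise only if two doses were selected and patients randomized between them.

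The conclusion rests on two assumptions: that Table 4 is complete as it appears, which the position of its footnote supports, and that no eCRF instruction outside the documents assigns these events a grade.

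**What to change.** Make the scale exhaustive in one of two ways:

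- Remove the clause in Severe that excludes immediately life-threatening events, and state that Severe covers every event above Moderate, including fatal ones.
- Keep the clause and add Life-threatening and Fatal levels above Severe.

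The first is the smaller change and is sufficient, since outcome data and the death listing already identify fatal events. The second also shows these events separately in the severity tables. Either way, bring the eCRF code list and completion guidelines into line, and set the categories of the Section 10.4.2 severity tables to match.

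The cost is an edit to one table and a check of the code list. The second option also needs a code-list update and one or two extra rows in the severity tables. Making the change before such events are graded avoids later queries to sites.
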